### 7.2 Efficacy assessment

The methods and timing for assessing, recording, and analysing efficacy parameters:

- Insulin profiles and CGM metrics will be assessed at each clinical review – Visit 1,2,3,4. They will also be monitored weekly using the Medtronic and Dexcom databases.
- Other clinical & metabolic outcomes will be measured at study start and study end – Visit 1 & 4
- Adherence to medication and adverse events will be determined at each clinical review – Visit 1,2,3,4
- Patient self-reported outcomes will be determined at the end of the study duration by means of a questionnaire

## 8 Assessment of Safety

### 8.1 Risks and benefits

All participants are on hybrid-closed loop therapy, whereby the patient's basal insulin delivery is adjusted on a 24h basis,. Hence any changes in glycaemia as a result of oral insulin use, will be offset by a change in the basal insulin delivered by the Hybrid Closed Loop system. Furthermore, oral insulin has been used with no increase in hypoglycaemic events.

The risk is attributed to glycaemic fluctuations, if any, as a result of combined closed loop and oral insulin therapy. This could include both hypoglycaemia and hyperglycaemia. Previous studies with oral insulin have not reported any serious adverse events (Product Investigation Brochure-Phase IIa DTY 0001 in T1DM); however two of the eight participants in the study reported headaches associated with oral insulin. Symptoms suggestive of a common cold were reported to a lesser degree. All participants will be monitored for side-effects like gastrointestinal intolerance, headaches and allergy, if any, during the study.

The benefits to the participants are that they may achieve better glycaemic control with a reduction in sub-cutaneous insulin requirements. They may also benefit from better metabolic outcomes in their lipid profile.

## 8.2 Safety

1. The safety parameters and the methods and timing for assessing, recording, and analysing safety parameters. Include a description of emergency procedures if applicable. Risk of hypoglycaemia/hyperglycaemia:

The risk of hypoglycaemia with oral insulin is negligible. However, any patient receiving insulin at any time has the potential to develop hyper or hypoglycaemia.

- a. The sensor glucose levels of all study participants are available to participants in real-time which will enable them to take appropriate clinical action as required. Participants will also be followed in real-time by research staff in the first three weeks of the study with commencement of oral insulin.
- b. Hybrid closed loop system is semi-automated and is dependent on the sensor glucose levels and basal insulin delivery will be adjusted based on sensor glucose readings. HCL is therefore expected to mitigate any risk of hypo/hyperglycaemia while on oral insulin

2. Risk of immediate allergic reactions with oral insulin

All participants will be monitored after the first dose for at least 30 minutes.

Emergency procedures:

- For severe hypoglycaemia, intramuscular glucagon can be administered.
- For ketosis > 0.6mmol/l with glucose > 15mmol/l, insulin (rapid-acting) is administered with an insulin pen.

This is taught to every family at the time of diagnosis of T1D and review of their knowledge is established in subsequent clinic follow-ups.

## 8.3 Data and Safety Monitoring Board

A data safety monitoring board, consisting of an endocrinologist, a statistician and a pharmacist, will be established to safeguard the interests of the trial participants, monitor the safety outcome measures, and monitor the overall conduct of the study. The board will receive and review information on the progress and accruing data and provide advice on the conduct of the trial to the investigators.

## 8.4 Adverse event reporting

Capsulin has been used effectively in type 2 diabetes management with no adverse outcomes. Further, as all participants are on hybrid-closed loop therapy, whereby the patient's insulin settings are adjusted on a 24h basis, minimal risks are expected during this study. Similarly, the risk of a serious adverse event is low. Any serious adverse event will be reported to Child Adolescent Health Service Human Research Ethics Committee using the Initial Serious Adverse Event Report Form within 72 hours of the event occurring or 24 hours if there is a material impact on the ethical acceptability of the study as considered by the principal investigator.

Adverse events will be elicited at each clinical review by means of clinician assessment and reviewing of the participant Logbooks. Further participants CGM and pump uploads are reviewed on a weekly basis for early pick-up of adverse events.

Adverse events are defined as:

- Gastrointestinal disturbances
- Skin rashes following oral insulin therapy and not related to pump/sensor therapy
- More than 40% increase in hypoglycaemia from baseline
- Hyperglycaemia with ketosis

Severe adverse events are defined as:

1. Severe hypoglycaemia: coma/convulsion/any episode requiring third party assistance for hypo treatment
2. Severe diabetic ketoacidosis: (venous pH < 7.2)
3. Any in-patient hospitalisation

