## 7 Assessment of Efficacy

### 7.1 Outcomes

1. Total insulin dose (units/kg/day) and the proportion of basal and bolus insulin
2. CGM metrics (13): 12-week CGM data will be collected for variables: Mean SG, % time in range 3.9 to 10 mmol/l, % time in hypoglycaemia (< 3 and < 3.9 mmol/l), % time in hyperglycaemia (>10 and >13.9 mmol/l), and glycaemic variability (coefficient of variation and standard deviation)
3. Auxology: Body mass index Z-scores
4. Metabolic bloods: Lipid profile (Triglycerides, cholesterol, LDL and HDL), Liver function test, HbA1c
5. Gut hormone (glucagon, glucagon-like polypeptide-1 (GLP-1) and glucose-dependent insulinotropic polypeptide (GIP)) responses to a standard meal challenge
6. Safety (Adverse events, Severe adverse events: Severe hypoglycaemia, diabetes ketoacidosis)
7. Recruitment and retention rates
8. Adherence to medication (track caps)
9. Patient-reported outcomes: experiences with oral insulin on appetite, GI disturbances and glycaemic outcomes

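### The adverse event definition in 8.4 is a closed list that leaves out headache and non-skin allergy, and the ethics reporting rule applies to *serious* events when only *severe* events are defined

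*Protocol*

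**What the plan says.** **Adverse events.** Section 8.4 states "Adverse events are defined as" and gives four items: "Gastrointestinal disturbances"; a rash after the capsule that the pump or sensor does not explain; hypoglycaemia up by over 40% on baseline; and high glucose with ketosis.

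**What is expected and watched for.** Section 8.1 reports, from the Phase IIa study in type 1 diabetes, that "two of the eight participants in the study reported headaches associated with oral insulin", with cold-like symptoms less often. It then promises: "All participants will be monitored for side-effects like gastrointestinal intolerance, headaches and allergy, if any, during the study". Section 8.2 has its own item, "Risk of immediate allergic reactions with oral insulin", with no restriction to the skin.

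**Expedited reporting.** Section 8.4 requires any *serious* adverse event to go to the ethics committee within 72 hours, or 24 hours if the principal investigator considers that the study's ethical acceptability is materially affected. The definition in the same section begins "Severe adverse events are defined as" and has three entries: severe hypoglycaemia, severe ketoacidosis (venous pH below 7.2) and in-patient admission.

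**Outcome and timing.** Outcome 6 in 7.1 counts adverse events and "Severe adverse events: Severe hypoglycaemia, diabetes ketoacidosis". Section 7.2 says "Adherence to medication and adverse events will be determined at each clinical review" and names Visits 1 to 4.

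**The concern.** The first aim in section 3 is preliminary data for a randomised trial of effectiveness and safety, and safety is a listed outcome of this pilot. What gets counted depends on the definition in 8.4. If staff apply it as written, the pilot can report no headache and no non-skin allergic adverse events even if participants have them, and the later trial would be planned on that profile.

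The reporting duty has a separate weakness. It rests on a word the protocol does not define. A team that uses the *severe* list in its place has no entry for a death or for a life-threatening event managed without admission.

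**Working it through.** No figure in the protocol is at issue, so the check is a comparison of sections.

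**1. Is the list closed?** Section 8.4 uses the language of definition and then lists four items. Nothing marks them as examples, and there is no catch-all entry. By contrast, the sentence in 8.1 on side-effects is worded as examples.

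**2. Do the events named elsewhere fit the list?**

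| Event | Where the protocol names it | In the four-item list? | In the *severe* list? |
|---|---|---|---|
| Gastrointestinal intolerance | 8.1 | Yes | Only if admitted |
| Headache | 8.1 (2 of 8, and to be monitored) | No | Only if admitted |
| Allergy shown as a rash | 8.1, 8.2 | Yes | Only if admitted |
| Allergy without a rash | 8.1, 8.2 | No | Only if admitted |

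Two kinds of event that the protocol says it will watch for, or names as a risk, are therefore outside its own definition of an adverse event.

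**3. Which term triggers the report?** The duty in 8.4 attaches to *serious*. The definition in 8.4 and the outcome in 7.1 both use *severe*. *Serious* is not defined in the protocol. Suppose the *severe* list was meant to serve. It then covers three things, and the following are not named:

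- death;
- a life-threatening event without admission, for example an immediate allergic reaction treated on site, which is a form of the risk named in 8.2.

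**4. Related wording.**

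- Severe hypoglycaemia is described in 4.9 by seizure, coma or use of glucagon, and in 8.4 by coma, convulsion or help from a third party. An episode treated by another person without glucagon, seizure or coma meets 8.4 but not 4.9.
- In the 4.8 schedule, the rows for Visits 2 and 3 carry an entry for capsule use and adverse events. The Visit 4 row does not, although 7.2 requires both there.

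**The case against.** **The gap is in classification, not capture.** Section 8.1 commits to monitoring headache and allergy, section 16.3 lists an adverse event logbook, and a safety board reviews accruing data (8.3). This stands. It limits the harm but does not remove it, because an event that is recorded and then judged against 8.4 still falls outside the count.

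***Severe* is a slip for *serious*.** The list sits in the reporting section and includes in-patient admission, which is a seriousness criterion and not a grade of intensity. Section 11.1 also commits to GCP. This reading is plausible, but the text does not say so, and under it death and life-threatening events without admission are still not named.

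**The two hypoglycaemia wordings serve different purposes.** Section 4.9 concerns whether a participant continues; 8.4 classifies events. That may be intended. If so, the protocol should say so, since both use the same term.

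**Stronger readings that a reader might infer, and that the protocol does not support:**

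- *Weeks 6 to 12 have no adverse event query.* The Visit 4 row alone suggests this. But 7.2 names Visit 4, 8.4 elicits events at each clinical review, and the notes to 4.8 provide weekly contact that includes safety.
- *Visit 5 lacks a required adverse event entry.* No section promises one there.
- *Abnormal liver tests would be lost.* They are a listed outcome in 7.1, measured at Visits 1 and 4, so they are reported whatever the label.
- *Section 7.1 sets a rival definition of ketoacidosis.* It is a short outcome label; 8.4 supplies the threshold.
- *Headache is almost sure to occur and be missed.* At 2/8 = 25%, 10 × 0.25 = 2.5 participants would be expected to have it, and the chance of at least one is 1 − 0.75^10 = 94%. But the exact 95% interval for 2/8 is 3.2% to 65.1%, so that chance runs from 28% to nearly 100%. If the study is the eight-adult one in 2.1, its rate comes from single doses of 150 IU and 300 IU, not 12 weeks of dosing. The mismatch exists at any rate, so the figure is illustration and not evidence.

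**Conclusion.** The point holds in two parts. First, the adverse event definition in 8.4 excludes headache and non-skin allergic reactions, which 8.1 and 8.2 treat as expected or possible. Second, the ethics reporting rule uses an undefined term, and the nearest definition names neither death nor a life-threatening event without admission.

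The conclusion assumes that staff apply the 8.4 wording literally. Under that assumption outcome 6 would under-count safety events, and a reportable event could be missed. How many cannot be estimated usefully from the protocol. The primary outcome, the sample size of 10 and the analysis are unaffected. The hypoglycaemia wording and the Visit 4 row are secondary matters to tidy at the same time. This should be fixed, but it does not undermine the study.

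**What to change.** - In 8.4, replace the closed list with an open GCP definition: any untoward medical occurrence after the first dose, whatever its relation to the drug. Section 11.1 already commits the trial to GCP.
- Keep the four current items, and add headache and allergic reaction, as solicited events asked about by name.
- Define *serious* by the standard GCP outcome criteria, which include death and life-threatening events. Tie the 72-hour and 24-hour rule to that definition, use the one term in 7.1 and 8.4, and record severity as a separate field.
- Reconcile the wording of severe hypoglycaemia in 4.9 and 8.4, or state that the two serve different purposes. Which wording applies is for the clinical investigators to decide.
- Add adverse event and adherence entries to the Visit 4 row of the 4.8 schedule, as 7.2 already requires.

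The cost is protocol wording and a line on the case report form or logbook. The drawback is that more adverse events will be listed, many of them probably minor or unrelated to the drug.

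### Section 8.4 counts a rash as an adverse event only if it is judged unrelated to the pump or sensor, so the rate of Capsulin rashes may be understated

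*Protocol*

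**What the plan says.** Section 8.4 of the protocol gives four adverse-event items:

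- "Gastrointestinal disturbances"
- "Skin rashes following oral insulin therapy and not related to pump/sensor therapy"
- "More than 40% increase in hypoglycaemia from baseline"
- "Hyperglycaemia with ketosis"

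A separate list defines severe events: severe hypoglycaemia, ketoacidosis with venous pH below 7.2, and any in-patient admission. Adverse events are elicited by clinician assessment and by review of participants' logbooks.

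Other sections bear on the point. Sections 4.3 and 4.4 say that everyone receives the same treatment. Sections 2.2, 5.2 and 6.2 put every participant on a Medtronic 670G or 770G closed-loop system. Section 4.8 sets up an additional Dexcom G6 for 670G users at Visit 1, and the first Capsulin dose is given at that visit. Section 8.1 lists allergy among the side-effects to watch for, and section 8.2 treats immediate allergic reaction as a separate risk.

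On ketosis, the emergency procedure in section 8.2 begins "For ketosis > 0.6mmol/l with glucose > 15mmol/l". Section 7.1 lists, as a CGM outcome, "time in hyperglycaemia (>10 and >13.9 mmol/l".

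**The concern.** Whether an event occurred and what caused it are separate questions. The rash item merges them: a rash judged to come from the pump or sensor is not an adverse event under section 8.4. A device explanation is available for every participant, and for those given the additional sensor a new adhesive device arrives on the day of first dosing. The people judging know that the participant is taking Capsulin, and the protocol gives no criterion or adjudication step.

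The research question in section 3 includes safety, and the pilot is meant to inform a randomised trial. If rashes are removed from the count by attribution, the next trial's designers may see a lower rash rate than the drug causes. In a sample of 10, a single reclassified case makes the difference between a signal and none.

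The ketosis item raises a smaller question. It requires hyperglycaemia but gives no glucose or ketone level and refers to no section that does.

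**Working it through.** **No figure to reproduce.** The protocol states no expected adverse-event rate and no safety precision target. The check is therefore a comparison of the definitions, followed by arithmetic to show scale.

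**Step 1: which items carry a condition?**

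| Item in 8.4 | Causality condition | Other condition |
|---|---|---|
| Gastrointestinal disturbance | none | none |
| Skin rash | must not be device-related | must follow oral insulin |
| Hypoglycaemia | none | rise above 40% from baseline |
| Ketosis | none | must come with hyperglycaemia |
| Three severe-event items | none | no glucose condition on ketoacidosis |

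One of the four adverse-event items (rash) depends on attribution. The ketosis item is a compound criterion and involves no causality judgement.

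**Step 2: what one lost case does.** Input: n = 10 (sections 9.1 and 9.2). Exact (Clopper-Pearson) 95% limits:

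- 1/10: lower limit 1 − 0.975^(1/10) = 0.3%. The upper limit solves (1 − p)^10 + 10p(1 − p)^9 = 0.025, giving p = 44.5%.
- 0/10: lower limit 0%. Upper limit 1 − 0.025^(1/10) = 30.8%.

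**Step 3: chance of recording at least one Capsulin rash.** Let p be the true risk per participant and f the share of such rashes attributed to a device. Both are assumptions, since the protocol gives neither. The chance is 1 − (1 − p(1 − f))^10.

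| p | f = 0 | f = 0.25 | f = 0.5 | f = 0.75 |
|---|---|---|---|---|
| 5% | 40.1% | 31.8% | 22.4% | 11.8% |
| 10% | 65.1% | 54.1% | 40.1% | 22.4% |
| 20% | 89.3% | 80.3% | 65.1% | 40.1% |
| 30% | 97.2% | 92.2% | 80.3% | 54.1% |

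For example, p = 20% and f = 0.5 gives 1 − 0.9^10 = 65.1%, against 1 − 0.8^10 = 89.3% with no filter.

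**Step 4: ketosis figures side by side.** Section 8.2 pairs ketones above 0.6 mmol/l with glucose above 15 mmol/l, as the trigger of an emergency procedure. Section 7.1 uses glucose above 10 and above 13.9 mmol/l, as CGM percent-time categories. Section 8.4 uses the word hyperglycaemia with no number and no cross-reference. An episode of ketosis at 12 mmol/l would meet the lowest of these glucose levels and neither of the other two.

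**The case against.** The strongest reply is that the filter has a sensible purpose. Participants use their own pump systems, so device-site reactions are a plausible background that would clutter the listing. With one arm there is no between-group bias. Staff could also err the other way and count a device rash as a drug rash. Section 8.1 reports headaches and cold symptoms in earlier use, not rash, so the values in step 3 are illustrative only. All of this stands, and it limits the point to a possible understatement of an absolute rate. It does not justify putting the judgement inside the definition, because a site field would identify device-site rashes just as well.

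A reader might infer more than the protocol supports in four respects:

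- **That the filters determine the whole safety count.** Attribution enters one of four items. The severe events carry no such condition.
- **That filtered rashes are lost and never reach the safety board.** Section 16.3 lists an adverse-event logbook, section 4.8 provides weekly contact to monitor safety, and sections 8.3 and 10.2 give the board access to data. The CRF is not shown and may already hold the needed fields. What can be said is that such rashes need not be counted or reported as adverse events.
- **That no glucose level for ketosis exists.** Section 8.2 pairs the two terms with numbers. The gap is that section 8.4 does not refer to it.
- **That ketosis at normal glucose is expected and would be missed.** The protocol predicts lower systemic insulin (section 2.1) and says that "any changes in glycaemia as a result of oral insulin use, will be offset by a change in the basal insulin", but it nowhere links this to ketosis without high glucose. The visit tables schedule no ketone measurement, so a new definition alone would not reveal it.

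**Conclusion.** The point holds for the rash item. As section 8.4 is worded, a rash that staff attribute to the pump or sensor is not an adverse event, whatever its true cause, and the absolute rate of Capsulin rash may be understated. The size cannot be estimated from the protocol. One filtered case changes the reported result from 1/10 (0.3% to 44.5%) to 0/10 (0% to 30.8%). Over assumed risks of 5% to 30% with half the drug rashes attributed to devices, the chance of recording at least one falls by about 17 to 25 percentage points (40.1% to 22.4% at the lowest risk, 97.2% to 80.3% at the highest, with the largest fall 65.1% to 40.1%). Those ranges rest wholly on the assumed p and f.

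The ketosis item is a secondary matter of reconciling section 8.4 with sections 8.2 and 7.1.

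**What to change.** In section 8.4, define the rash item as any skin rash after the first dose, whatever its cause. Record body site and judged relatedness to Capsulin, pump and sensor as separate CRF fields. Report the all-cause count first and the related count second, so that a later reader can review the attribution.

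For the ketosis item, reconcile sections 8.4, 8.2 and 7.1 and state in 8.4 which glucose and ketone levels, if any, apply to event counting. Record the concurrent glucose with any ketone value obtained. This concerns counting only and leaves the emergency procedure in section 8.2 unchanged.

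The cost is two reworded lines and a few CRF fields, if these do not already exist. The downside is a few device-site rashes in the listing, which the site field identifies.

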## 8.5 Follow-up of Adverse Events

The type of follow-up required after an adverse event will be determined by the doctor on the study team according to clinical need.

# 9 Data Management, Statistical Analysis and Record Keeping

## 9.1 Statistics and Interim Analysis

This will be a pilot study with 10 participants. This sample size was chosen based on providing estimates of the mean and variance of outcome measures to within a degree of precision acceptable to inform the power calculation for a definitive trial. Appropriate descriptive statistics (frequencies (%), mean (SD), median (IQR)) will be presented for all sociodemographic and clinical characteristics of the sample. Mean and standard deviation, along with their 95% confidence interval, will be presented for continuous/interval outcome measures of interest in each phase and for the paired difference between baseline and end of study. The SD for the primary outcome (change in average total daily insulin delivered subcutaneously) will be presented along with the upper value of a one-sided 80% confidence interval.

## 9.2 Sample Size

10 participants with complete data for the 12 week study – including adherence to the study drug, insulin profiles, CGM metrics, clinical and metabolic outcome measures. All participants will be seen at PCH, as both FSH and SCGH are only used for recruitment,

## 9.3 Study Power and Significance

Alpha of 5%

#### **9.4 Statistical plan deviations:**

Any deviations to the original statistical plan will be reported to relevant ethics committees as an amendment to the scientific protocol and in the manuscript.

#### **9.5 Selection of participants for analyses:**

All participants who have complete data for the 12w study duration – including adherence to the study drug, insulin profiles, CGM metrics, clinical and metabolic outcome measures; will be included in the analyses.

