**4.9 Trial Termination**

Study participation is voluntary, and participants may withdraw at any time.

In general, once a participant is in the study, he/she will remain in the study unless the investigator believes it is not safe for the participant to continue. The criteria below will be used to determine safety:

1. Severe hypoglycaemia (seizure or coma or any episodes requiring glucagon).
2. Severe diabetic ketoacidosis (venous ph <7.2)

3. Non-compliance with the medication which in the judgment of the investigator increases risk for the participant

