#### 5.4 Participant withdrawal criteria

Participants can withdraw at any time from the study, without having to provide a reason for doing so. Those who withdraw from the study after commencing on oral insulin, will be asked to return all unused capsules to the research unit. They will not require any follow-up as the insulin is a quick acting insulin, without any carry-over effects.

Participants who withdraw from the study will need to be replaced, as the study is powered for a sample size of 10 with completed data.

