#### **9.7 Procedures for missing, unused and spurious data:**

No imputation will be made on missing, unused, and spurious data i.e. only valid data will be used as collected.

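### Section 9.5 fixes one completers-only analysis set, which fits safety, adherence and retention badly and could select the SD meant to plan the later trial

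*Protocol*

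**What the plan says.** Section 9.5 is the only place in the protocol that selects participants for analysis. It takes "All participants who have complete data for the 12w study duration", lists the domains that must be complete (adherence, insulin profiles, CGM, and clinical and metabolic measures), and says that people with complete "clinical and metabolic outcome measures; will be included in the analyses". It makes no exception for safety or feasibility outcomes.

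Section 9.2 defines the sample as 10 people with complete data on the same domains. Section 5.4 fits this: "Participants who withdraw from the study will need to be replaced, as the study is powered for a sample size of 10 with completed data". It also says that those who leave need no follow-up.

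Section 4.9 lists criteria that guide the investigator's judgement that continuing is unsafe. They include "Severe hypoglycaemia (seizure or coma or any episodes requiring glucagon" (the bracket continues no further), severe ketoacidosis with venous pH below 7.2, and "Non-compliance with the medication which in the judgment of the investigator increases risk for the participant".

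The outcomes in 7.1 include safety (naming severe hypoglycaemia and ketoacidosis), "Recruitment and retention rates", and adherence by track cap. Section 9.1 names the change in average daily subcutaneous insulin as primary and reports its SD with an upper one-sided 80% limit. The estimates are meant to inform the power calculation of a definitive trial.

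**The concern.** The aims in section 3 are preliminary data for a randomised trial of effectiveness and safety, and acceptability to participants. People who stop early carry much of the information on safety and acceptability, and the stated rule leaves them out. Three listed outcomes are affected directly, because part of what they measure also decides who is analysed: severe events can lead to stopping, risky non-compliance can lead to stopping, and retention is itself the condition for entry. The primary outcome is affected less directly, through the requirement that unrelated domains be complete.

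This is not detail left to a later analysis plan. The protocol fixes a set, and 9.4 treats departures from the statistical plan as amendments to be reported. Counting withdrawn participants at the analysis stage would therefore be a deviation.

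**Working it through.** **The plan's own figure.** N = 10 cannot be reproduced: the protocol gives alpha of 5% but no effect size, SD, power, precision target or dropout rate. What 10 completers deliver can be computed.
- Upper one-sided 80% limit for the SD: s × √[(n−1)/χ²(0.20; n−1)] = s × √(9/5.38) = 1.29 s.
- 95% half-width for a mean: t(0.975; 9)/√10 = 2.262/3.162 = 0.72 SD.

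Both describe sampling error only. Neither allows for selection.

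**Retention and severe events.** Let w be the number who start, leave and are replaced (assumed, 1 to 4). Retention among starters is 10/(10+w). Exact limits are Beta(0.025; x, n−x+1) and Beta(0.975; x+1, n−x). The last column takes the extreme case in which all w left after a severe event and no completer had one.

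| w | Retention among starters (95% CI) | Severe events among starters (95% CI) |
|---|---|---|
| 1 | 10/11 = 91% (59 to 99.8%) | 1/11 = 9% (0.2 to 41%) |
| 2 | 10/12 = 83% (52 to 98%) | 2/12 = 17% (2 to 48%) |
| 3 | 10/13 = 77% (46 to 95%) | 3/13 = 23% (5 to 54%) |
| 4 | 10/14 = 71% (42 to 92%) | 4/14 = 29% (8 to 58%) |

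In the 9.5 set every row reads 10/10 retained and 0/10 severe events (95% CI 0 to 31%).

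**Adherence.** Anyone who stops early has no complete 12-week record, so their track-cap data fall outside the set. The size cannot be computed from the protocol.

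**Completeness across domains.** If five domains were each 95% complete and independent (assumed), 0.95⁵ = 0.774 of participants would qualify, and 10/0.774 = 12.9, so about 13 would be needed. Section 5.4 replaces only those who withdraw. Someone who finishes but lacks one domain is neither replaced nor analysed. With 9 or 8 analysed, the SD multiplier rises from 1.29 to 1.32 or 1.35.

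**The planning SD.** Two illustrations, both at an assumed 20% loss.
- *Loss correlated with the outcome.* For a normal variable that loses its worst 20%, the remaining variance is v = 0.583. With correlation ρ between loss and the insulin change, the SD ratio is √[1 − ρ²(1 − v)] = 0.98, 0.95 or 0.89 for ρ = 0.3, 0.5 or 0.7. The squares, 0.96, 0.90 and 0.80, are the ratios of planned to needed N at a fixed target difference.
- *Stoppers have no effect.* Give completers SD 1 and a mean change of 1 SD, and stoppers a mean of 0. With p = 0.2, the variance in all starters is (1−p)·1 + p·σ² + p(1−p)·1², where σ is the stoppers' SD. For σ = 1 it is 0.8 + 0.2 + 0.16 = 1.16, so the completers' SD is too small (1/√1.16 = 0.93). For σ = 0 it is 0.8 + 0 + 0.16 = 0.96, so the completers' SD is slightly too large (1/√0.96 = 1.02).

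Selection can therefore move the SD either way.

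**The case against.** **The rule can be read more kindly.** Section 9.5 never says that completers alone are analysed, its list of domains does not name safety or retention, and a retention rate makes sense only over people enrolled. A sensible analyst might count everyone without being told. That is fair, but no passage gives another denominator, and 9.2 and 5.4 both confirm a completers' sample.

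**Stopping is not automatic.** Under 4.9 it rests on the investigator's judgement, and non-compliance counts only where it raises risk. Severe hypoglycaemia in 8.4 extends to any episode needing third-party help, which is wider than the 4.9 wording. Completers may therefore have imperfect adherence, lesser adverse events, a hospital admission, or even a severe event after which they continued. A reader might infer that outcomes are estimated only in people who did well; the text does not support that. Only events that lead to stopping are lost.

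**Oversight is intact.** Adverse events are elicited at each review, serious ones go to the ethics committee (8.4), and the safety board monitors safety (8.3). A reader might infer that the publication would hide such events, but section 14 places no such limit. The loss is from the stated analysis set.

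**There is no contradiction with 9.7.** It says "only valid data will be used as collected" and rules out imputation. A reader might take this as a promise to use all valid data, but it says only that invalid data are not used, which is compatible with complete-case selection.

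**The later trial is not shown to be undersized.** A reader might infer this from the second illustration: at 20% loss with σ = 1, N would need to be 1.16/0.8² = 1.81 times larger. Of that, 1/0.8² = 1.56 comes from dilution of the effect and only 1.16 from variance. The loss rate, the 1 SD effect, the absence of effect in stoppers and the later trial's analysis population are all assumptions.

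**Conclusion.** The point holds as a badly fixed analysis rule. Retention is uninformative in the 9.5 set by construction, and a severe event that leads to stopping cannot appear in a safety summary built on that set. Both follow from the wording and need no assumption. How far the figures would move does need one: with 2 or 3 replaced starters, retention is 83% or 77% rather than 100%.

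For adherence, the omission of early stoppers is clear but its size is unknown. For the SD of insulin change, selection is only a possibility. The protocol gives no dropout rate or pattern, and the illustrations range from an SD 11% too small to one 2% too large. The clinical stopping criteria are not at issue.

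**What to change.** Reword 9.5, and 5.4 to match:

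1. **Safety and adherence:** summarise adverse events and adherence in everyone who takes at least one Capsulin dose.
2. **Feasibility:** report retention among all who start, keeping replaced participants in the denominator and giving reasons for stopping. Report recruitment among those approached or screened.
3. **Other outcomes:** analyse each one, including the primary insulin-dose change and its SD, in all participants with valid baseline and on-treatment data for that outcome. Show completers as a supportive analysis.

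Replacement to reach 10 completers can stay, provided that the person replaced is still counted.

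The third item recovers insulin data from people who lack another domain, and pump data up to the time of stopping. Because 5.4 asks for no follow-up after withdrawal, it cannot supply week-12 HbA1c, lipids or meal-challenge results for those who left, so the report should state how many are missing.

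The cost is wording in two sections and a few extra tables, with no extra participants. Reported retention, adherence and SD may look less favourable.
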